11.6.5. Physical Finding Analyses

Physical examination data at each evaluation will be listed. Subjects with clinically significant abnormal findings will be noted in the data listing.

11.6.6. Other Safety Analyses

11.6.6.1. Bleeding

Bleeding events will be summarized as the following categories: sICH, any ICH, or non-ICH major bleeding. The number and percentage of subjects experiencing these bleeding events will be tabulated by treatment. Results from placebo-treated subjects will be pooled across cohorts.

11.6.6.2. Neurologic function

Neurologic function will be assessed using the NIHSS. Raw values of the NIHSS score will be presented graphically by subject, and will also be summarized by treatment. Change from baseline values will be summarized. The number and percentage of subjects of 0 or 1 point of postdose NIHSS and 4 points or more improvement of NIHSS will be tabulated by scheduled time of evaluation and treatment. Pooled placebo data of all cohorts will be summarized.

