2. STUDY OBJECTIVES AND HYPOTHESES

2.1. Study Objectives

2.1.1. Primary Objective

The primary objective of the study is to assess the safety and tolerability of DS-1040b (IV infusion over 6 hours) in subjects with AIS within 3 to 8 hours after stroke symptom onset.

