2.1.2. Secondary Objectives

The secondary objectives of the study are as follows:

- To assess the plasma and urinary PK of DS-1040b in subjects with AIS.
- To assess the effect of DS-1040b on fibrinolysis biomarkers in subjects with AIS.
- To assess the effect of DS-1040b on recanalization at 24 hours in subjects with AIS.
- To assess the effect of DS-1040b on neurological outcome by using the National Institute of Health Stroke Scale (NIHSS) and functional outcome by using the modified Rankin Scale (mRS) in subjects with AIS.

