3.1.3. Study Endpoints

The endpoints for this study include the following:

- Safety parameters:

Serious adverse events, TEAEs, physical examination findings, vital sign measurements, standard clinical laboratory parameters (including serum chemistry, hematology, urinalysis, and coagulation parameters), and electrocardiogram (ECG) parameters.

Other safety parameters will include bleeding events and neurologic function. Bleeding events will be assessed and categorized as sICH, any intracranial hemorrhage (ICH), or non-ICH major bleeding. Neurologic function will be measured using the NIHSS.

- Pharmacokinetic parameters:

Standard noncompartmental PK parameters will be assessed. Plasma samples for PK assessments will be taken at multiple timepoints in the study. Additionally, a PK sample may also be obtained outside of the specified timepoints during the study if deemed clinically necessary. Urine PK samples will also be collected and evaluated in the study.

- Pharmacodynamic parameters:

Pharmacodynamic analysis for TAFIa antigen and clot lysis along with D-dimer and total TAFIa activity will be performed. Remaining blood samples will be used for post-hoc TAFIa inhibition-related coagulation biomarker assessments.

Recanalization will be assessed during the study.

- Other parameters:

An assessment of functional outcome using the mRS will be performed during the study.

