4.1.1. Inclusion Criteria

Subjects must satisfy all of the following criteria to be included in the study:

1. Subjects have a clinical diagnosis of ischemic stroke MCA occlusion (M1 or M2), as demonstrated by CT or MR angiography.
2. Men and women 18 to 80 years of age, inclusive.
3. Subjects have stroke symptom onset within 3 to 8 hours before initiation of study drug administration. For subjects with a wake-up stroke, symptom onset time refers to the last time the subject was known to be well.
4. Subjects have a NIHSS score > 4 and < 22 .
5. Subjects have a body weight of 50 kg to 120 kg, inclusive.
6. Subjects, or their legally authorized representative, must give written informed consent to participate in the study prior to participating in any study-related procedures. A separate written informed consent is required for collecting a blood sample for genotyping.

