7. EFFICACY ASSESSMENTS

Efficacy will not be evaluated in this study.

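### NIHSS is analyzed as a safety measure, but its only planned subject counts are for benefit; no scale-based count of NIHSS worsening by dose and visit is planned

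*Combined protocol and SAP*

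**What the plan says.** - Section 2.1.1: "The primary objective of the study is to assess the safety and tolerability of DS-1040b (IV infusion over 6 hours) in subjects with AIS".
- Section 3.1.3: "Other safety parameters will include bleeding events and neurologic function", the latter measured by NIHSS. Section 2.1.2 also makes the drug's effect on neurological outcome, again by NIHSS, a secondary objective. The scale therefore has two roles.
- Section 7: "Efficacy will not be evaluated in this study".
- Section 11.6.6.2, under Other Safety Analyses: "Raw values of the NIHSS score will be presented graphically by subject, and will also be summarized by treatment". It continues: "Change from baseline values will be summarized". The subject counts are for "subjects of 0 or 1 point of postdose NIHSS and 4 points or more improvement of NIHSS will be tabulated", by scheduled time and treatment.
- Section 11.2: quantitative data get mean, SD, median, minimum, maximum and number of observations for each active dose arm and pooled placebo. Missing data are not imputed.
- Section 11.6.6.1 tabulates subjects with sICH, any ICH or non-ICH major bleeding by treatment. Under Section 9.9.1, sICH requires hemorrhage to be the predominant cause of the deterioration.
- Section 11.6.1 counts subjects with treatment-emergent adverse events (TEAEs) and serious events by system organ class and preferred term, and summarizes adverse events by treatment.

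**The concern.** A safety scale should be able to show harm as readily as benefit. Other measures in this plan can: laboratory values get low/normal/high shift tables (Section 11.6.2), QT intervals get absolute and increase thresholds (Section 11.6.4), and TIMI reperfusion gets a baseline-to-posttreatment shift table (Section 11.5.2). NIHSS, the safety scale closest to the disease, gets favorable categories only.

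The two indirect counts leave a gap. Neurologic decline not mainly caused by hemorrhage is outside sICH by definition. It reaches the TEAE table only if the investigator judges it an adverse event (Section 9.2.1), after general, non-specific questioning (Section 9.1). Because events are reported by diagnosis, similar declines can scatter across preferred terms. No rule in the text makes a given NIHSS rise an adverse event.

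At stake is the reading of tolerability by dose. The report could show how many subjects improved on the scale at each dose, but not how many got worse.

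**Working it through.** **Denominators.** From Table 3.1, total enrollment is 8 + 8 + 3×16 = 64 up to 5×16 = 80, which reproduces the stated range. Active subjects number 6 + 6 + 36 = 48 up to 60, and pooled placebo 2 + 2 + 12 = 16 up to 20. Each active dose arm has 6 or 12 subjects.

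**Are the two planned counts distinct?** Section 4.1.1 requires: "Subjects have a NIHSS score > 4 and < 22". In whole points this is 5 to 21. From the lowest eligible baseline to the highest score in the 0-or-1 category the fall is 5 − 1 = 4. So every eligible subject who reaches 0 or 1 has also improved by at least 4. The categories are nested, and neither records harm.

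**Do the other planned NIHSS summaries determine the number who worsened?** Take two hypothetical 12-subject sets of change from baseline (negative = improvement):

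- Set A: −8, −8, −8, −5, −3, −1, 2, 3, 3, 8, 8, 8
- Set B: −8, −8, −8, −5, −3, −3, 4, 4, 5, 6, 7, 8

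| Statistic | A | B |
|---|---|---|
| Sum | −33 + 32 = −1 | −35 + 34 = −1 |
| Mean = sum/12 | −0.08 | −0.08 |
| Sum of squares | 227 + 214 = 441 | 235 + 206 = 441 |
| SD = √[(441 − 1/12)/11] | 6.33 | 6.33 |
| Median | (−1 + 2)/2 = 0.5 | (−3 + 4)/2 = 0.5 |
| Minimum, maximum | −8, 8 | −8, 8 |
| Improved by 4 or more | 4 | 4 |
| **Worse by 4 or more** | **3 (25%)** | **6 (50%)** |

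The raw-score summaries need not separate the sets either. If every subject starts at 12, an eligible score, postdose scores are 12 plus the change. They run from 4 to 20 in both sets, with the same mean, SD and median, and nobody scores 0 or 1. Only the by-subject plots would differ.

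**Precision of the missing row.** With no events, the exact (Clopper-Pearson) 95% upper limit is 1 − 0.025^(1/n).

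- 0/6: 0 to 46%
- 0/12: 0 to 26.5%
- Pooled placebo, 0/16: 0 to 20.6%; 0/20: 0 to 16.8%
- 2/12, exact interval: 2.1 to 48.4%

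**The case against.** **Worsening is counted elsewhere.** A reader might infer that neurologic worsening is never counted by dose. The documents do not support that. Section 11.6.6.1 counts sICH by treatment, and Section 11.6.1 counts TEAEs and serious events, including an ongoing event that worsens after dosing. Infarct extension or edema recorded as an adverse event would be counted. What is missing is a count based on the scale itself.

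**The summaries can show harm.** This also stands in part. The maximum change, the SD and the plots would all reveal a subject who worsened, and in some arms they fix the count. Suppose nine subjects improve by 4 and three worsen by 6: mean −1.5, median −4, 9/12 improved. The worsening may look hidden, but the changes sum to −18 and nine improvers contribute −36 or less, so the other three sum to at least +18. With a maximum of +6, each must be +6. Sets A and B show that this recovery fails in general. The plots leave each reader to choose a threshold after seeing the data.

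**The improvement counts belong.** Section 7 might be read as making them out of place. Section 2.1.2 gives them a purpose, and nested thresholds are not an error. They should stay.

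**Decisions do not rest on this table.** Escalation uses bleeding, other adverse events, laboratory data and the stopping rules (Sections 3.1.6 and 11.9), and the analysis is descriptive throughout. That limits the consequence but does not remove the gap in reporting.

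**The detail may be in a later plan.** Section 11 defers methods to an analysis plan finalized before database lock, and the text supplied contains no separate plan. If that plan has a worsening table, the point is met.

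**Conclusion.** The point holds in this form: the plan states no scale-based count of NIHSS worsening by dose and visit, while its only NIHSS subject counts run toward benefit and are nested for eligible baselines. Worsening is counted only through sICH and reported adverse events. The remaining NIHSS tables can be identical for arms in which 25% and 50% of subjects worsened by 4 or more points.

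This is a cheap improvement, not a flaw in design or conduct. Sample size, allocation and stopping rules are untouched.

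Assumptions: the two sets are constructed to show what is possible and do not predict the trial's data. The 4-point threshold is assumed because it matches the improvement criterion in Section 11.6.6.2 and the figure in the sICH definition in Section 9.9.1. Nesting assumes a baseline within the eligible range.

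**What to change.** In Section 11.6.6.2, or in the analysis plan to which Section 11 defers:

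1. Keep both improvement counts; they serve the secondary objective.
2. Add the number and percentage of subjects with an NIHSS increase of 4 or more points from predose. Report it at 6 hours, 24 hours, Day 5/discharge and Day 30, and at any scheduled postdose time, by dose and pooled placebo.
3. Show deaths before each visit as a separate count. Without imputation, these subjects would otherwise drop out of the table.
4. If the row is split by hemorrhage, split only by whether ICH was centrally confirmed at any time. The only scheduled postdose imaging is at 24 hours (Section 6.2) and other scans are discretionary (Section 8.2), so a visit-by-visit split would class unscanned subjects as free of ICH.
5. First reconcile the direction of the scale. Section 9.9.1 describes deterioration as a decrease in NIHSS of 4 or more points, whereas Section 11.6.6.2 treats scores of 0 or 1 as the good result, so lower is better.

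The cost is one extra descriptive row per visit plus the deaths count. NIHSS is already scheduled at these times and ICH is already centrally assessed. The downside is wide intervals in arms of 6 or 12, so the row should be read as description only.

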11.7. Other Analyses

Functional outcome will be assessed using the mRS. Raw values of mRS scores will be presented graphically by subject, and will also be summarized by treatment. Change from baseline values (inclusion/exclusion criteria) will be summarized. The number and percentage of subjects of 0 or 1 point of postdose mRS will be tabulated by scheduled time of evaluation and treatment. Pooled placebo data of all cohorts will be summarized.

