4.1.2. Exclusion Criteria

Subjects who meet any of the following criteria will be disqualified from entering the study:

1. Subjects have evidence of intracranial hemorrhage on noncontrast CT (or MR).
2. Subjects have symptoms of subarachnoid hemorrhage, even with normal CT.
3. Subjects have evidence of large MCA territory infarction (sulcal effacement or blurring of gray-white junction in greater than 1/3 of MCA territory).
4. Subjects have prior non-traumatic intracranial hemorrhage.
5. Subjects have known arteriovenous malformation or aneurysm.
6. Subjects have evidence of active bleeding.
7. Subjects have platelet count < 100,000.
8. Subjects have INR > 1.7.
9. Subjects have used heparin within 48 hours or have an elevated partial thromboplastin time.
10. Subjects have used a nonvitamin K antagonist oral anticoagulant such as dabigatran, rivaroxaban, apixaban, or other factor Xa inhibitors within 48 hours.
11. Subjects have used fondaparinux or low molecular weight heparin at an anticoagulation dose within 48 hours.
12. Subjects with anticipated use of heparin, or fondaparinux or low molecular weight heparin, or nonvitamin K antagonist oral anticoagulant such as dabigatran, rivaroxaban, apixaban, or other factor Xa inhibitors within 48 hours of randomization.
13. Subjects have blood pressure > 185/110 mmHg, or require aggressive medication to maintain blood pressure below this limit (routine medical treatment is allowed to lower the blood pressure below this limit).
14. Subjects have had intracranial surgery, clinically significant head trauma (in the opinion of Principal Investigator), Alteplase treatment, or a previous stroke within 3 months.
15. Subjects have had major surgery within 14 days.
16. Subjects have had gastrointestinal or genitourinary bleeding in the last 21 days.
17. Subjects have had a lumbar puncture (or epidural steroid injection) within 14 days.
18. Subjects have a preexisting disability classified by mRS > 1.
19. Subjects have an estimated glomerular filtration rate (using Modification of Diet in Renal Disease [MDRD] equation) < 60 mL/min/1.73 m².
20. Subjects have baseline hemoglobin < 10.5 g/dL.

21. Subjects have a positive pregnancy test. Serum pregnancy tests will be performed in women of childbearing potential (childbearing potential is assumed in women up to 55 years of age).

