6.1.1. Predose

The following assessments will be performed predose:

- Obtain written (ie, signed and dated) informed consent
- Assess inclusion/exclusion criteria
- Record medical history information (including mRS, if possible)
- Record prior/concomitant medication
- Obtain a blood sample for follicle stimulating hormone evaluation
- Obtain a serum sample for pregnancy testing in women of childbearing potential (childbearing potential is assumed in women up to 55 years of age)
- Perform a complete physical examination including weight (can be estimated by the subject, family members, or the Principal Investigator)
- Perform a non-contrast CT or MR, followed by angiography (after hemorrhagic stroke is ruled out)
- Administer the NIHSS
- Obtain supine vital sign measurements
- Perform a 12-lead ECG in triplicate
- Obtain blood samples for safety laboratory assessments (serum chemistry and hematology) (Section 9.5)
- Obtain a urine sample for urinalysis (Section 9.5)
- Obtain blood samples for PT, INR, aPTT, and fibrinogen (Section 9.5)
- Obtain PD blood sample (TAFIa activity, clot lysis, TAFI antigen, D-dimer) (Section 8.2)
- Assess subjects for adverse events
- Obtain PK blood sample

6.1.2. 0 Hour

The following assessments will be performed at 0 hour:

- Administer DS-1040b
- Start collection of urine for PK assessments

An optional PGx sample can be obtained at any time after dosing.

6.1.3. 0.5 Hours Postdose

The following assessments will be performed 0.5 hours after dosing started:

- Obtain supine vital sign measurements
- Perform a 12-lead ECG in triplicate
- Obtain blood samples for PT, INR, aPTT, and fibrinogen (Section 9.5)
- Obtain PD blood sample (TAFIa activity, clot lysis, D-dimer) (Section 8.2)
- Obtain PK blood sample

6.1.4. 3 Hours Postdose

The following assessments will be performed 3 hours after dosing:

- Obtain supine vital sign measurements
- Perform a 12-lead ECG in triplicate
- Obtain PK blood sample

6.1.5. 6 Hours Postdose

The following assessments will be performed 6 hours after dosing:

- Obtain supine vital sign measurements
- Perform a 12-lead ECG in triplicate
- Obtain blood samples for PT, INR, aPTT, and fibrinogen (Section 9.5)
- Obtain PD blood sample (TAFIa activity, clot lysis, TAFI antigen, D-dimer) (Section 8.2)
- Administer the NIHSS
- Assess subjects for adverse events
- Obtain PK blood sample

6.1.6. 9 Hours Postdose

The following assessment will be performed 9 hours after dosing:

- Obtain PK blood sample

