11.2. General Statistical Considerations

The primary analysis is to assess the safety and tolerability of DS-1040b in subjects with AIS.

In all the analyses, data will be tabulated with descriptive summary statistics for exploratory and hypothesis-generating purpose. No imputation will be performed for dropouts or missing data.

All quantitative PK, PD, and safety data will be tabulated with descriptive summary statistics: arithmetic mean; standard deviation (SD); median, minimum and maximum values; number of observations. In addition, geometric mean and the coefficient of variation (%CV) for geometric mean will also be calculated for AUC_{0-inf} , AUC_{last} , and C_{max} . Frequency counts and percentages will be provided for categorical data. Summaries will be provided for each active dose arm and on the pooled placebo arm. When data are available for both predose and postdose assessments, summaries will be provided on predose assessments, postdose assessments, and change from predose to postdose assessments, respectively.

Results from placebo-treated subjects will be pooled across cohorts

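### mRS change from a prestroke baseline of 0 or 1 adds almost nothing to the raw scores, and read literally the plan leaves deaths out of every mRS summary

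*Combined protocol and SAP*

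**What the plan says.** Functional outcome on the mRS is part of a secondary objective (Section 2.1.2). Section 11.7 plans three summaries:

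- Raw scores: "Raw values of mRS scores will be presented graphically by subject, and will also be summarized by treatment".
- Change: "Change from baseline values (inclusion/exclusion criteria) will be summarized". The synopsis says the same.
- Responders: "The number and percentage of subjects of 0 or 1 point of postdose mRS will be tabulated by scheduled time of evaluation and treatment".

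The only eligibility criterion that uses the mRS is exclusion 18 in Section 4.1.2: "Subjects have a preexisting disability classified by mRS > 1". Before dosing, Section 6.1.1 has the site do the following: "Record medical history information (including mRS, if possible". The mRS is otherwise administered at Day 5 or discharge, Day 30 and Day 90 (Sections 6.5, 6.6.1 and 6.6.2). The Schedule of Events in Section 17.5 likewise marks those three occasions and no predose one.

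On missing data, Section 11.2 states: "No imputation will be performed for dropouts or missing data". Section 4.2.1 includes death among the reasons for withdrawal from the study. Neither Section 11.1 nor Section 11.7 names the analysis set for the mRS, and no section gives a score or a denominator for subjects who have died.

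On presentation, Section 11.2 states: "Summaries will be provided for each active dose arm and on the pooled placebo arm". It describes the purpose thus: "data will be tabulated with descriptive summary statistics for exploratory and hypothesis-generating purpose".

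**The concern.** There are two issues, and the second matters more.

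First, a table headed change from baseline is normally read as recovery or deterioration under treatment. Here the baseline predates the stroke, so the change mostly measures what the stroke did. The NIHSS table in Section 11.6.6.2 carries the same label but starts from a predose score taken after the stroke, so the two tables would look alike and mean different things. The mRS baseline may also be absent for some subjects, because the site is asked to record it only where it can.

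Second, a subject who dies before Day 30 or Day 90 has no later mRS assessment. If death counts as a dropout and dropouts are not imputed, that subject leaves all three summaries, including the two that need no baseline. The loss is not random with respect to outcome: it removes the worst results. The stopping rules in Section 3.1.6 show that symptomatic intracranial hemorrhage is the main feared harm. If fatal harm rose with dose, the survivors at the higher doses would give a flattering picture of functional outcome.

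**Working it through.** The plan states no effect size, SD, mortality or missing rate for the mRS, so it has no figure to reproduce on this point. Arm sizes come from Table 3.1: 12 active in Cohorts 3 to 5, and 6 or 12 in Cohorts 1 and 2. Pooled placebo is 64/4 = 16 to 80/4 = 20. The documents do not list the mRS categories; I assume 0 to 5 for survivors and 6 for death.

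**Range of the change.** Let B be the prestroke score (0 or 1) and Y the postdose score.
- Lowest change: 0 − 1 = −1. The only possible improvement is from 1 to 0.
- Highest change: 5 − 0 = +5 in survivors, or 6 − 0 = +6 if death is scored 6.

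**Within-arm meaning.** Assume Day 90 probabilities for scores 0 to 6 of 0.08, 0.14, 0.14, 0.16, 0.22, 0.10, 0.16 on placebo (mean 3.24) and 0.14, 0.20, 0.16, 0.15, 0.17, 0.07, 0.11 on active (mean 2.66). Let the share q with B = 1 run from 0 to 0.5.
- Mean change = mean(Y) − q: +2.74 to +3.24 on placebo and +2.16 to +2.66 on active.
- Despite the assumed benefit, 76% to 86% of active subjects show a positive change (worsening) and at most about 7% a negative one.

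**Between-arm contrast.** With A for active and P for placebo:

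mean change(A) − mean change(P) = [mean Y(A) − mean Y(P)] − [mean B(A) − mean B(P)].

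The last bracket has expectation 0 if the prestroke mix is the same in both groups, and SE = √(q(1 − q)(1/n_A + 1/n_P)). At its maximum, q = 0.5:
- 12 against 20: √(0.25 × (1/12 + 1/20)) = 0.18 points.
- 6 against 16: √(0.25 × (1/6 + 1/16)) = 0.24 points.

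In 20,000 simulated comparisons of 12 against 20 per value of q, the contrast averaged about −0.58 on both raw and change scores. Its SD was 0.68 to 0.69 raw and 0.68 to 0.71 for change, and the two contrasts correlated at 0.97 to 1.00. The change table therefore carries nearly the same comparison as the raw table, slightly more noisily.

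**Unrecorded baselines.** If a share m is not recorded (assumed), n falls to n(1 − m) and the SE rises by a factor 1/√(1 − m). This touches the change table only.

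| m | 12 becomes | 20 becomes | SE increase |
|---|---|---|---|
| 10% | 10.8 | 18 | 5% |
| 20% | 9.6 | 16 | 12% |
| 40% | 7.2 | 12 | 29% |

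**Deaths.** Take an arm of n = 12 with k = 4 subjects at mRS 0–1 and d deaths, the survivors averaging 2.5 (all assumed). With deaths dropped, the proportion is k/(n − d) and the mean is 2.5. With deaths kept, the proportion is k/n = 4/12 = 33% and the mean is [2.5(n − d) + 6d]/n.

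| d | 0–1, deaths dropped | 0–1, deaths kept | Mean, deaths dropped | Mean, deaths kept |
|---|---|---|---|---|
| 0 | 4/12 = 33% | 33% | 2.50 | 2.50 |
| 1 | 4/11 = 36% | 33% | 2.50 | (27.5 + 6)/12 = 2.79 |
| 2 | 4/10 = 40% | 33% | 2.50 | (25 + 12)/12 = 3.08 |
| 3 | 4/9 = 44% | 33% | 2.50 | (22.5 + 18)/12 = 3.38 |

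Two arms with the same 4 responders thus report 33% with no deaths and 40% with two. At d = 2 the mean moves by 3.08 − 2.50 = 0.58, as large as the drug effect assumed above. Unlike the 0-or-1 baseline, this shift does not cancel between arms when the numbers of deaths differ.

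**The case against.** The strongest reply is that little depends on the change table. Each dose is shown beside pooled placebo, so a drug effect would still appear as a smaller average worsening. A reader might infer that the change measures stroke disability instead of a drug effect, or that every arm must worsen alike whatever the drug does. The documents do not support either reading: the between-arm contrast is almost untouched, and a subject who ends at 0 or 1 can have a change of 0 or −1. Section 11.7 also already plans two summaries that need no baseline. This part of the reply stands.

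A reader might also infer that many subjects drop out for want of a baseline. That is not shown. Exclusion 18 requires prestroke disability to be judged for every subject, so the loss could be zero. What remains is a mismatch between needing the score for eligibility and recording it only where possible.

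On deaths, the reply is that the plan never calls them missing, that a death scored 6 is an observed outcome rather than an imputed one, that Section 11 defers detailed methods to an analysis plan finalized before database lock, and that deaths are reported as SAEs and listed (Sections 9.1 and 11.6.1). All of this is fair: exclusion of deaths follows from a literal reading, not from an explicit statement. But Section 4.2.1 does place death among withdrawals, and nothing in the text supplied says otherwise. A separate listing of deaths does not correct a proportion calculated without them.

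**Conclusion.** The point holds as a minor one. Within an arm, mRS change mainly reflects the index stroke and adds almost nothing to the raw scores. Against pooled placebo, the baseline adds chance noise with an SE of at most about 0.18 points (12 against 20) or 0.24 points (6 against 16). That bound assumes a similar prestroke mix across the sequential cohorts whose placebo subjects are pooled.

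The gap on deaths is the more consequential part. It affects all three summaries and can favor the arm with more deaths: 40% against 33% for two deaths in 12, or 36% to 44% for one to three. These figures are illustrative, since the documents give no expected mortality and no mRS distribution.

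No test or decision rests on the mRS. The analyses are descriptive, Sections 7 and 11.4 set efficacy aside, and escalation under Section 11.9 rests on bleeding, other adverse events and safety laboratory data. The risk is a misleading description of a secondary objective in arms of 6 or 12.

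**What to change.** - In Section 11.7 and the synopsis, replace the mRS change summary with the full mRS distribution, 0 to 6 with death as 6, at Day 30 and Day 90, by dose and for pooled placebo.
- Keep the mRS 0–1 count and percentage, with deaths in the denominator. Name the analysis set, and show subjects missing for other reasons as a separate count.
- State that a known death is an outcome and falls outside the no-imputation rule in Section 11.2.
- Report prestroke mRS as a baseline characteristic. Reconcile Section 4.1.2 with Sections 6.1.1 and 17.5 so that the score on which eligibility depends is recorded for every subject.

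The cost is protocol and analysis-plan wording and one table in place of another. Adverse events, including deaths, are already recorded to Day 90 (Section 9.1), so the only added data item is a firm predose record of the prestroke score. The downside is that survivors and deaths are combined on one scale; showing the whole distribution keeps the death category visible. The change should be made before the analysis plan is finalized.
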